#### 5 INVESTIGATIONAL PLAN

### 5.1 Overall Study Design

[figure not shown]
This is a multi-center, randomized (1:1), double-blind, vehicle-controlled, parallel-group study evaluating trifarotene cream in treating acne-induced hyperpigmentation in patients with acne. Approximately 120 randomized subjects aged 13-35 are planned, at approximately 20 study centers in the United States and Europe. Target enrollment should include an approximate distribution of Fitzpatrick Skin Types, 30% light skin (I-III) and 70% dark skin (IV-VI).

Subject eligibility will be evaluated over a 28-day screening period. Qualifying subjects will complete Baseline assessments and be randomized (1:1) to Trifarotene or Vehicle for a 24-week treatment period. Subjects will be provided skin care products including Cetaphil® Gentle Skin Cleanser for washing the face twice daily (morning and evening); Cetaphil® Dermacontrol Moisturizer with SPF 30 for use daily on the face (morning) and to be re-applied to face before sun exposure, and Cetaphil® Moisturizing Lotion for extra moisturizer as needed. If a subject experiences persistent dryness or irritation, the investigator may consider a reduced application frequency for the topical study drug, over a maximum of 2 weeks, within the first four (4) weeks of the treatment period (Section 5.4.8 – Dose Modification of Topical Study Drug).

Subjects who do not require a washout period may complete the Screening and Baseline assessments on the same day. Subjects who initially fail screening may be re-screened once, provided the reason for screen failure is not due to acne severity (IGA) or lesion counts.

Subjects will return to the clinic for safety and efficacy assessment at Weeks 1, 2, 4, 8, 12, 16, 20 and 24. Study procedures and assessments are performed according to the schedule of assessments (Section 5.1.1).

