# 5.2 Discussion of Study Design

This study will evaluate acne-induced hyperpigmentation during treatment of acne vulgaris subject with trifarotene 50  $\mu$ g/g cream versus vehicle cream over 24 weeks.

This is a Phase 4 clinical study to assess the effect of commercially-marketed AKLIEF® (trifarotene)  $50 \mu g/g$  cream, when used according to its labeling information (indication, selected population, dose regimen) for the treatment of acne lesions to evaluate the risk of post-inflammatory pigment formation.

All subjects will receive skincare products for daily use, with frequent clinic visits for ongoing subject evaluation and to ensure safety. Topical treatment with a vehicle-control along with a skincare regimen has shown some degree of clinical benefit in acne studies.

Subject safety will be appropriately monitored throughout the 24-week treatment period with 8 scheduled post-Baseline visits which occur every 4 weeks, which include two early visits for additional safety checks and subject counselling (Week 1 and Week 2).

A multicenter, long-term safety study with once daily treatment for 1-year showed trifarotene 50  $\mu$ g/g cream to be well-tolerated, without undue safety risks (Blume-Peytavi 2019).

A 24-week treatment period is utilized knowing acne is a chronic skin condition, which should be sufficient to assess clinical effect on the basis of the following points:

- Post-inflammatory hyperpigmentation appears secondarily to acne lesions and may correspond to resolution of these lesions.
- It is generally agreed in acne clinical studies that a 12-week treatment period is sufficient to evaluate the efficacy on the acne lesions. An additional 12 weeks is included to further evaluate the clinical outcomes associated with treatment of acne lesions.

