## 5.4.2 Instructions for Use – Study Drugs and Non-Investigational Products

Table 3: Guidelines for Using Study Drugs and Non-Investigational Products

[figure not shown]
	Trifarotene Cream				
	OR				
Trifarotene Vehicle Cream					
Study Drug Usage	
 
Apply a thin layer to the face once daily, in the evening. The face should be washed and patted dry, before use.
 
One pump actuation should be enough to cover the face (i.e., forehead, cheeks, nose, and chin).
 
				
	The Investigator may instruct alternate day regimen application of the topical study drug (detailed subject instruction will be provided) and re-evaluate at each visit to modify accordingly following the Baseline visit. Refer to Section 5.4.8 – Dose Modification of Topical Study Drug.				
	Non-Investigational Product Use Guidelines *				
Cetaphil® Gentle Skin C	Cleanser: Topical, wash face, twice daily, in the morning and evening.				
Cetaphil® Dermacontrol day, reapply every two h	Moisturizer SPF 30: Topical, apply after morning cleansing. If sun exposure during the nours.				
Cetaphil® Moisturizing Lotion: Topical, if extra moisture is needed, apply as needed.					
Duration of administrati	on for the above products: 24 weeks				

\* These are guidelines for non-investigational product use and will not be recorded as protocol deviations. Subjects will be counselled on the importance of using non-investigational products per the study guidelines, throughout the study. Compliance and protocol deviation reporting will apply only to study drug products. Alternative cleanser and moisturizers are not permitted, only the supplied non-investigational products to be used.

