### **5.4.8 Dose Modification**

If a subject experiences persistent skin dryness or irritation, the Investigator may consider a reduced application frequency for the topical study drug in the first 4 weeks of the study, for a maximum duration of 2 weeks. Subjects should be instructed to capture all missed topical applications in the dosing calendar. Sites will record the timing and details of a prescribed dose reduction for topical medication in source records.

Signs and symptoms of local cutaneous irritation will be considered as Adverse Events if they are severe enough to lead to permanent discontinuation of topical study drug or if they require the use of concomitant treatment including OTC products (other than moisturizers). Refer to Section 6.3.4 for further details on local tolerability assessment.

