#### WARNINGS AND PRECAUTIONS

#### 5.1 Skin Irritation

Patients using AKLIEF Cream may experience erythema, scaling, dryness, and stinging/burning. Maximum severity of these reactions typically occurred within the first 4 weeks of treatment, and severity decreased with continued use of the medication. Depending upon the severity of these adverse reactions, instruct patients to use a moisturizer, reduce the frequency of application of AKLIEF Cream, or suspend use temporarily. If severe reactions persist the treatment may be discontinued.

Avoid application of AKLIEF to cuts, abrasions, or eczematous or sunburned skin. Use of "waxing" as a depilatory method should be avoided on skin treated with AKLIEF Cream.

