4.6 Analysis Sets

The efficacy summaries and analyses will be based on the **Intent-to-Treat (ITT) population** defined as all randomized subjects. If a subject is allocated the incorrect study drug as per the study randomization list, subjects will be summarized and analyzed 'as randomized' i.e., by randomized treatment group.

For the primary efficacy variable, a sensitivity analysis will be performed on the **Per Protocol (PP) Population** to assess the robustness of the study conclusions to the choice of population. The PP Population is defined as any subjects in the ITT population who had compliance to the study drug between 80% and 120% and assessments of the primary endpoint at Baseline and Week 24, without any major deviations that could have a significant effect on the efficacy of the study drug (e.g., errors in drug assignment, use of prohibited medications). Subjects will be summarized and analyzed 'as randomized' i.e., by randomized treatment group.

The safety summaries and analyses will be based on the **Safety Population**. The Safety Population is defined as comprising the ITT population subjects who applied/took the study drug at least once. If a subject is allocated the incorrect study drug as per the study randomization list, subjects will be summarized and analyzed 'as treated' i.e., by allocated treatment group.

Upon database release, protocol deviation and analysis populations outputs will be produced and reviewed. An analysis set classification meeting will be arranged to discuss the outputs and to decide which subjects and/or subject data will be excluded from certain analyses. Decisions made regarding the exclusion of subjects and/or subject data from analyses will be made prior to unblinding and will be documented and approved by Sponsor.

Number and percentage of subjects in each analysis population will be summarized by treatment group and overall, (Analysis set: All Randomized Subjects)

A by-subject listing of analysis populations details will be provided. This listing will be presented by treatment group and will include center, subject identifier, inclusion/exclusion flag for each population and reason for exclusion from each population. All subjects screened will appear on this listing. If subject data has been partially excluded, visit will also appear on this listing.

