4.9.2 Compliance and Drug Accountability

The compliance will be calculated for each visit and globally as:

Actual applications

Planned Applications – Missed Applications due to Prescribed Dose Reductions \times 100

CCL

For the overall compliance:

- Overall actual applications will be derived as the sum of actual applications at each visit. For treated subjects with no drug accountability information, overall actual applications will be calculated as Date of Last Treatment as collected in the End of Treatment form minus Date of First Treatment as collected in the End of Treatment form plus 1. If Date of Last Treatment is not collected in the End of Treatment form, overall actual applications will be set to 1.
- Overall planned applications will be derived as date of study completion/discontinuation minus date of baseline visit.
- Overall missed applications due to prescribed dose reductions will be derived as the sum of missed applications due to prescribed dose reductions at each visit.

Number and percentage of subjects compliant defined as having a compliance between 80% and 120% will be summarized by treatment group and overall.

Additionally, compliance expressed in percentage and by category (<80%; 80%-120%; >120%) will be summarized by visit and globally and will be presented for each treatment group and overall based upon the ITT population.

By-subject listings will be presented for compliance and drug accountability. .

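### SAP 4.9.2 credits every prescribed missed dose without the protocol's 2-week limit, so an over-limit reduction scores as full compliance and meets the per-protocol compliance criterion

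*SAP*

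**What the plan says.** **Compliance.** SAP 4.9.2 divides actual applications by planned applications less those missed because of prescribed dose reductions, for each visit and globally. For the global figure, the deduction "will be derived as the sum of missed applications due to prescribed dose reductions at each visit". No limit on duration, timing or number is attached. Overall planned applications are the days from the baseline visit to completion or discontinuation. Protocol 5.4.6.4 derives compliance from expected and recorded doses and mentions no deduction.

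**PP set.** SAP 4.6 requires "compliance to the study drug between 80% and 120" percent, primary-endpoint assessments at Baseline and Week 24, and no major deviation likely to affect efficacy. The PP analysis is one of four sensitivity analyses of the primary endpoint (SAP 4.10.2.2).

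**Dose reduction.**
- Protocol 5.4.8 permits "a reduced application frequency for the topical study drug in the first 4 weeks of the study, for a maximum duration of 2 weeks".
- Protocol 5.1 has the same limit: "over a maximum of 2 weeks, within the first four (4) weeks of the treatment period".
- Protocol 5.4.2, Table 3, lets the investigator instruct an alternate-day regimen and "re-evaluate at each visit to modify accordingly following the Baseline visit". That sentence contains no time limit, but the next one reads "Refer to Section 5.4.8 – Dose Modification of Topical Study Drug".

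**The concern.** The PP compliance criterion should identify subjects who used the drug broadly as planned. With an unlimited deduction, each missed dose that was prescribed leaves the denominator as well as the numerator, so a prescribed reduction can never lower the score, however long it lasts. The limit in Protocol 5.1 and 5.4.8 has no counterpart in the SAP formula.

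The wording of Table 3 adds to this. A site that relies on its sentence about each visit could regard a later or longer reduction as allowed, prescribe it, and not report a deviation.

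At stake are the compliance tables, which would show such a subject as fully compliant, and the PP analysis, which could include the subject as adequately treated.

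**Working it through.** The plan gives no worked compliance figure to reproduce, so the check applies its own formula.

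**Inputs**
- Once-daily application for 24 weeks (Protocol 5.4.2). With the Week 24 visit on Day 169 (SAP 4.2.6), planned applications P = 169 − 1 = 168.
- PP range 80% to 120% (SAP 4.6).
- Limit: 2 weeks within the first 4 (Protocol 5.1 and 5.4.8). On alternate days, 14 days cost 7 applications.

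**Formula.** Compliance = 100 × actual / (P − prescribed misses). If all misses, m, are prescribed, this is 100 × (P − m)/(P − m) = 100% for any m below P. The result does not depend on P being 168.

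**Alternate-day use, with no other misses**

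| Period of alternate-day use | Missed | Applied | SAP 4.9.2 as written | No deduction | Deduction limited to 2 weeks (7 doses) |
|---|---|---|---|---|---|
| 14 days, within the limit | 7 | 161 | 161/161 = 100% | 161/168 = 95.8% | 161/161 = 100% |
| 56 days | 28 | 140 | 140/140 = 100% | 140/168 = 83.3% | 140/161 = 87.0% |
| 67 days | 33 | 135 | 135/135 = 100% | 135/168 = 80.4% | 135/161 = 83.9% |
| 68 days | 34 | 134 | 134/134 = 100% | 134/168 = 79.8% | 134/161 = 83.2% |
| 80 days | 40 | 128 | 128/128 = 100% | 128/168 = 76.2% | 128/161 = 79.5% |
| Week 4 to Week 24 (140 days) | 70 | 98 | 98/98 = 100% | 98/168 = 58.3% | 58.3% (nothing falls inside the limit) |
| All 24 weeks | 84 | 84 | 84/84 = 100% | 84/168 = 50.0% | 84/161 = 52.2% |

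Except in the Week 4 to Week 24 row, the last column assumes that two weeks of the reduction fall inside the permitted window.

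**Where PP status changes.** Without any deduction, 80% of 168 is 134.4, so 33 misses pass and 34 fail; 34 misses are 68 days of alternate-day use, about 9.7 weeks. With a 7-dose credit, the line is at 168 − 0.8 × 161 = 39.2 misses, about 78 days or 11 weeks. As written, prescribed misses alone never reach the line.

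**Lowest exposure that passes as written, with alternate-day use throughout.** With 16 inadvertent misses on top, 68/84 = 81.0%, which passes with 68/168 = 40.5% of planned doses. One more miss gives 67/84 = 79.8%, which fails.

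**Likely arm.** The appended label reports moderate or severe facial erythema in 28.4 + 6.2 = 34.6% on active and 6.8 + 0.8 = 7.6% on vehicle, and dryness in 29.7 + 4.8 = 34.5% and 7.6%. Reductions for irritation are thus probably more common on active. These are irritation rates and do not show how many reductions exceed the limit.

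**Possible shift in the PP estimate (illustration only).** Assume that 5% to 20% of active PP subjects are on a long reduction and get half the planned 1.0-point effect. The estimate moves by 0.05 × 0.5 = 0.025 to 0.20 × 0.5 = 0.10 points, toward no difference. With SD 1.4 and 42 per arm (SAP 4.13), the standard error is 1.4 × √(2/42) = 0.31, so the shift is 0.08 to 0.33 standard errors. Neither the 5% to 20% nor the halved effect comes from the documents.

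**The case against.** Several counter-arguments carry weight.

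- **Table 3 is not a freestanding rule.** A reader might infer that the protocol licenses alternate-day dosing through Week 24. The text does not support that, because Table 3 refers straight to 5.4.8, and re-evaluation at each visit fits the visits at Weeks 1, 2 and 4. What stands is loose wording that a site could misread. If 5.4.8 governs, an over-limit reduction is a deviation, yet the SAP still scores it 100%.
- **Other apparent conflicts are weak.** The four weeks run from the study in 5.4.8 and from the treatment period in 5.1, but no drug is dispensed before Baseline. The label mentions reducing frequency or suspending use under its warnings, while its dosage section says once daily; a narrower trial limit does not contradict a label warning.
- **PP entry needs more than compliance.** The major-deviation clause and the classification meeting before unblinding (SAP 4.6) may exclude such subjects. It cannot therefore be said that half-dose subjects will be in the PP set. The deviation specification is, however, a separate document (SAP 4.5.3), and the examples in SAP 4.6 are assignment errors and prohibited medication.
- **Reductions are visible.** SAP 4.9.3 summarizes and lists their frequency, duration and missed applications, and SAP 4.11.1 reports mean daily amount by pump weight. This discloses the problem but does not decide PP membership.
- **The deduction has a use.** In a Week 2 to Week 4 interval, a permitted alternate-day fortnight would score 7/14 = 50% without it. This argues against dropping the deduction altogether, but not against limiting it for the overall figure.
- **Long reductions may be rare.** The label says facial irritation scores peaked at Week 1 and then fell.

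**Conclusion.** The concern holds in a limited form. SAP 4.9.2 lets a reduction beyond the protocol's limit count as full compliance, up to 100% for a subject who applied 50% of planned doses, and neither document says that such a reduction is a major deviation.

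The effect is confined to the compliance tables and the PP sensitivity analysis. On prescribed misses alone, it changes PP status only for alternate-day use of more than about 9 weeks; shorter reductions matter only together with inadvertent misses. The number of subjects affected is unknown.

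A reader might infer that the primary result is biased or that the PP analysis could make the effect look more robust than it is. The documents do not support either. The primary analysis uses all randomized subjects and makes no use of compliance, and if less drug means less effect, under-dosed active subjects pull the PP estimate toward no difference.

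The figures assume 168 planned applications, but the 100% score does not depend on this. The point is worth correcting because the change is cheap.

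**What to change.** 1. **SAP 4.9.2.** For overall compliance and the PP criterion, deduct only prescribed missed applications that fall within the protocol's stated limit, and count those outside it as missed. Keep the fully adjusted figure for the by-visit descriptive tables. Alternate-day use for 24 weeks would then score 52.2%, while a permitted fortnight still passes comfortably with or without the credit.
2. **Protocol.** Reconcile Table 3 with 5.1 and 5.4.8 so that the permitted period and maximum duration read the same in all three. The sponsor decides which rule applies, and the SAP limit then follows it.

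The cost is one sentence in the SAP and an alignment of wording in the protocol. Duration and missed applications are already planned outputs (SAP 4.9.3), and sites record the timing of reductions in source records (Protocol 5.4.8). The downside is small: a few subjects with long reductions, probably more of them in the active arm, may leave the PP set. That is a selection effect to acknowledge when the PP result is reported.

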4.9.3 Prescribed Dose Reductions

The following information will be summarized for each treatment group and overall based upon the ITT population:

- Subjects with Prescribed Dose Reduction since the Last Scheduled Visit
- Reasons for Prescribed Dose Reduction
- Application/Dose Frequency during the Prescribed Dose Reduction
- Duration of Prescribed Dose Reduction (days)
- Missed Applications due to Prescribed Dose Reductions

A by-subject listing of Prescribed Dose Reductions will be presented.

4.10 Efficacy Evaluation

Summaries based on observed cases (OC) will be provided for all primary and secondary efficacy endpoints. For these summaries, no data will be imputed. All primary and secondary efficacy summaries will be based upon the ITT population.

Line plots and bar charts over time based on observed cases (OC) will be provided for PIH Overall Disease Severity scores and IGA scores. Line plots over time based on observed cases (OC) will be provided for total, inflammatory and non-inflammatory lesions. These plots and charts will be based upon the ITT population and no data will be imputed.

Moreover, line plots over time based on imputed data will be provided for PIH Overall Disease Severity scores. These plots will be based upon the ITT population and data will be imputed using Multiple Imputation (MI) under the Missing At Random (MAR) assumption (see section 4.10.1.3).

4.10.1 Analysis and Data Conventions

This study is designed to test for superiority. The null hypothesis for the treatment comparison will be that there is no difference between Trifarotene 50 μ g/g cream and vehicle cream in Absolute change from Baseline in PIH Overall Disease Severity scores at Week 24. The alternative hypothesis will be that there is a difference.

 $\begin{cases} H_0: \mu_{\text{Trifarotene 50 } \mu\text{g/g}} - \mu_{\text{Vehicle}} = 0 \\ H_a: \mu_{\text{Trifarotene 50 } \mu\text{g/g}} - \mu_{\text{Vehicle}} \neq 0 \end{cases}$

The hypothesis test for the primary efficacy endpoint will be evaluated on the ITT population at the significance level $\alpha = 0.05$.

4.10.1.1 Multi-center Study

Prior to database lock, a review of the blinded data will be performed to determine the size of each center. If there are centers with less than 8 randomized subjects, then these centers will be pooled in order to carry out the analyses. The process of combining centers will be based on the ITT population, and same pooling will be repeated for PP population.

Pooling will be country based. First, centers of each country will be sorted by latitude zone (based on geographic and climatic similarities), number of randomized subjects (descending order) and center number (ascending order). Pooling will start with combining the largest of the set of small centers of a latitude zone of a country with the smallest center within the same latitude zone of that country. If there is a further need to combine data (the size of the pooled centers includes less than 8 subjects), the next smallest center will be combined with the next largest of the small centers, until the criterion of a minimum of 8 subjects is met. The process will continue until all pooled centers have a minimum of 8 subjects within the same latitude zone of a country will be pooled with the last pooled center within the same latitude zone of that country. The pooled centers and the remaining original unpooled clinical centers will be referred to as 'analysis centers' and will be used as stratification factor in the statistical analyses.

If at the start of pooling any latitude zone of a country has less than 8 subjects in the ITT population in total, then centers will be added to the list of small centers in another latitude zone of that country and then combined as above. This decision will be documented in clinical report.

4.10.1.2 Adjustments for Covariates

The primary efficacy analysis and secondary efficacy analyses will be adjusted for the following baseline covariates:

- 1. Analysis Center
- 2. Baseline score

